9.8.4 Other Assessments

Not applicable.

[figure not shown]
[figure not shown]
9.9 Health Economics OR Medical Resource Utilization and Health Economics

[figure not shown]
Health Economics/Medical Resource Utilization and Health Economics parameters will not be specifically captured and evaluated as a primary part of this study.

10 STATISTICAL CONSIDERATIONS

10.1 Sample Size Determination

The planned sample size is approximately 150 participants per treatment group. Assuming that about 3/4 of the participants would be SE+, this would lead to approximately 112 SE+ participants per treatment group.

To preserve an overall type I error rate of 5%, the primary endpoint and secondary efficacy endpoints will be assessed using a hierarchical testing approach. The hierarchy in secondary endpoints is determined by the order they are listed in [Table 4-1](#) and is as follows:

- 1) Proportion of participants meeting ACR50 response at Week 24 in the SE+ subpopulation.
- 2) Proportion of participants achieving DAS28-CRP remission (< 2.6) at Week 24 in the SE+ subpopulation.
- 3) Proportion of participants meeting ACR50 response at Week 24 in the full study population.
- 4) Proportion of participants achieving Clinical Disease Activity Index (CDAI) remission (≤ 2.8) at Week 24 in the SE+ subpopulation.
- 5) Mean change from baseline in participant-reported pain at Week 24 in the SE+ subpopulation.

Each endpoint will be tested with a 2-sided alpha level of 5% if the endpoints at a higher level in the hierarchy are statistically significant. The testing will stop as soon as an endpoint is not statistically significant.

Assuming that the difference between treatment groups in the primary endpoint will be statistically significant, the sample size of 112 per arm will have [REDACTED] power to detect a difference in DAS28-CRP remission in SE+ population at Week 24 (Day 169) under the assumption of a response rate of [REDACTED] as observed in the SE+ subgroup in IM101567.

Assuming that both ACR50 and DAS28-CRP remission are statistically significantly different between the treatment groups in the SE+ population, there will be [REDACTED] power to detect a difference in ACR50 between the treatment groups in the entire population (SE+ and SE-) with a sample size of 150 per group and assuming response rates of [REDACTED] as in IM101567.

Assuming all endpoints higher in the hierarchy are statistically significantly different between the treatment groups, the sample size of 112 per arm will have [REDACTED] power to detect a difference in CDAI remission (≤ 2.8) at Week 24 if the underlying remission rate is [REDACTED] per treatment group as observed in the SE+ subgroup of IM101567.

Assuming all endpoints higher in the hierarchy are statistically significantly different between the treatment groups, a sample size of 112 per group will have [REDACTED] power to detect a difference

between the groups in mean change from baseline in participant-reported pain at Week 24. This assumes that the underlying mean change from baseline is [REDACTED] as observed in the SE+ subgroup of IM101567, with a common standard deviation of [REDACTED], using a 2-group t-test with 0.05 2-sided significance level.

10.2 Populations for Analyses

The populations for the purpose of analyses are defined in Table 10.2-1.

Table 10.2-1: Populations for Analyses

Population	Description
Enrolled	All participants who sign informed consent form.
Modified Intent-to-treat Analysis Population	All randomized participants who receive at least 1 dose of study medication. This population will exclude participants who are randomized, but not treated. Analyses using the mITT analysis population will group the participants according to the treatment group to which they are randomized. All efficacy analyses will use the mITT population.
Intent-to-treat Population	All randomized participants, also those who are never treated. Participants who were randomized and never treated and did not return for any assessments after discontinuation (ie, lost to follow-up or withdrew consent) will be excluded from the ITT analysis population. This population may be used for a sensitivity analysis of the primary endpoint. Analyses using the ITT analysis population will group the participants according to the treatment group to which they are randomized.
Per-protocol Analysis Population	All randomized participants who receive at least 1 dose of study medication, excluding the participants with relevant protocol deviations. Relevant protocol deviations are those that potentially may impact the primary efficacy outcome. The criteria for relevant protocol deviations will be defined in the SAP. Analyses using the PP analysis population will group the participants according to the treatment group to which they are randomized.
As-treated Analysis Population	All participants who receive at least 1 dose of study medication. Analyses using the as-treated analysis population will group the participants on an as-randomized basis unless a participant received the incorrect medication for the entire period of treatment. In that case, the participant will be analyzed in the treatment group associated with the incorrect medication they received (“as-treated”). The as-treated analysis population will be used for safety analyses of the SBTP.
Cumulative Abatacept Population	All randomized participants who receive at least 1 dose of abatacept during the SBTP and/or the OLTP. All participants of the as-treated population will be included, except for participants treated with adalimumab in the SBTP who never entered the OLTP.
Subgroup of SE+ Participants	The subgroup of participants that are SE+ at baseline.

Abbreviations: ITT, intent-to-treat; mITT, modified intent-to-treat; OLTP, Open-label Treatment Period; PP, per-protocol; SBTP, Single-blind Treatment Period; SC, subcutaneous; SE+, shared epitope-positive.

10.3 Statistical Analyses

A description of the participant population will be included in a clinical study report, including subgroups of age, gender, and race. Demography and baseline disease characteristics will be presented by randomized treatment group and overall for the intent-to-treat (ITT) population. Continuous variables such as age and weight will be summarized using means, standard deviations, median, and ranges. Categorical variables such as gender, race, and region, will be summarized using frequencies.

10.3.1 Efficacy Analyses

Hierarchical testing of the primary and key secondary endpoints, as described in [Section 10.1](#), will be applied. P-values will be presented for the treatment comparisons of the primary and key secondary endpoints. Statistical analysis methods for efficacy analyses are provided in Table 10.3.1-1.

Table 10.3.1-1: Efficacy Statistical Analyses

Endpoint	Statistical Analysis Methods
Proportions	The binary efficacy endpoints (eg, the proportion of participants meeting ACR50 response at Week 24) will be analyzed with a logistic regression including treatment in the model. The OR along with its 95% CI will be provided. A missing responder value at Day 169 due to discontinuation or for other reasons will be imputed as a nonresponder. For analysis of variables in the overall population (SE+ and SE-), the stratification variable SE +/- will also be included as a factor in logistic regression model. For analysis of proportions that are based on a cutoff value of continuous variable (eg, remission defined as DAS28-CRP < 2.6) for which a corresponding value is measured at baseline (baseline DAS28-CRP measurement), the analysis model will also include the continuous baseline covariate.
Mean Change From Baseline	Mean changes from baseline in continuous variables will be analyzed using a longitudinal repeated measures analysis. The model will include the fixed categorical effects of treatment, day (is a windowed time point), stratification variable SE +/- (as appropriate), treatment-by-day interaction, and covariate of corresponding baseline and baseline-by-day interaction. An unstructured covariance matrix will be used to represent the correlation of the repeated measures within each participant. The parameter estimations will be based on the assumption of data being MAR and using the method of REML. The difference in adjusted LSMEANS between abatacept and adalimumab at the primary time point, Week 24, and corresponding 95% CI will be provided. For the key secondary variable of mean change from baseline at Week 24, the P-value will be based on the longitudinal model.

Abbreviations: ACR50, 50% improvement in American College of Rheumatology criteria; CI, confidence interval; LSMEANS, least-squared means; DAS28-CRP, Disease Activity Score 28-joint count calculated using C-reactive protein; MAR, missing at random; OR, odds ratio; REML, restricted maximum likelihood; SAP, Statistical Analysis Plan; SE-, shared epitope; SE+, shared epitope-positive.

Details of the efficacy analysis during the OLTP will be provided in the SAP.

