In the IM101235 study (AMPLE; ClinicalTrials.gov: NCT00929864),⁴³ RA patients treated with abatacept or adalimumab, on background of MTX therapy, demonstrated similar improvement across all efficacy outcomes over 2 years of treatment.⁵⁴ In a post-hoc analysis, the subset of participants enrolled in AMPLE with early, rapidly progressive disease (defined as ≤ 6 months' disease duration; seropositive for RF and/or ACPAs and had ≥ 1 radiographic erosion) were compared for efficacy outcomes.⁵⁵ When comparing abatacept with adalimumab, over 2 years of treatment, the adjusted mean change in $DAS28$ -CRP from baseline at Day 365 was -2.58 (95% confidence interval [CI] -2.99 to -2.17) vs -1.68 (95% CI -2.10 to -1.25) and in Health Assessment Questionnaire Disability Index (HAQ-DI) from baseline at Day 365 was -0.70 (95% CI -0.90 to -0.51) vs -0.50 (95% CI -0.71 to -0.30), respectively. In this subset of RA patients with early, seropositive disease, abatacept appears to be more efficacious than adalimumab.

In another post-hoc analysis of the AMPLE study, study participants were tested for baseline anti-CCP-2 levels.⁴⁵ CCP-2 is a routine clinical assay for assessing ACPAs. Participants were divided according to CCP-2 concentrations in quartiles. Patients in the higher quartiles, especially Q4, had a better clinical response to abatacept than to adalimumab, independent of any other clinical characteristics. Here also, seropositivity and magnitude of this auto-antibody response was associated with better response to abatacept therapy.

The IM101567 trial (Early AMPLE; ClinicalTrials.gov: NCT02557100) was a mechanistic head-to-head study assessing changes in the immune profile with abatacept (125 mg weekly) and TNF-alpha blockade (adalimumab, 40 mg biweekly), both in combination with MTX, in 80 adult participants with early RA (symptoms for ≤ 12 months) who had an inadequate response to

MTX.⁴⁴ Numerically higher ACR responses were seen with abatacept vs adalimumab after 24 weeks of treatment; 50% improvement in ACR (ACR50) estimate of difference % was 25 (95% CI 2 to 46; see [Figure 3.1-1](#)). The vast majority (76%) of participants randomized in the Early AMPLE study were SE+ and showed higher differential efficacy to abatacept vs adalimumab compared with the overall population (estimate of difference % for ACR50 was 32 [95% CI 7 to 55] and for DAS28-CRP was 27 [95% CI 1 to 50]; see [Figure 3.1-2](#)).

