4 OBJECTIVES AND ENDPOINTS

Table 4-1: Objectives and Endpoints

Objective	Endpoint
Primary	

 To demonstrate the superiority in efficacy of abatacept compared with adalimumab, both on background MTX, in achieving clinical response (ACR50) at Week 24, in early, seropositive (RF+ and ACPA+) RA patients with the SE HLA Class II risk alleles (ie, SE+). 	
 Proportion of SE+ participants meeting ACR50 response at Week 24
Key Secondary	

 To compare the efficacy of abatacept with adalimumab, both on background MTX, in achieving clinical remission criteria (DAS28-CRP remission) at Week 24 in early, seropositive RA patients with the SE HLA Class II risk alleles (ie, SE+). 	
 Proportion of SE+ participants achieving DAS28-CRP remission (DAS28-CRP < 2.6) at Week 24

 To compare the efficacy of abatacept with adalimumab, both on background MTX, in achieving clinical response (ACR50) at Week 24 in the whole study population of early, seropositive RA patients. 	
 Proportion of whole study population participants meeting ACR50 response at Week 24

Table 4-1: Objectives and Endpoints

Objective	Endpoint

 To compare the efficacy of abatacept with adalimumab, both on background MTX, in achieving clinical remission criteria (CDAI remission) at Week 24 in early, seropositive RA patients with the SE HLA Class II risk alleles (ie, SE+). 	
 Proportion of SE+ participants achieving CDAI remission (CDAI ≤ 2.8) at Week 24

 To compare the efficacy of abatacept with adalimumab, both on background MTX, in achieving improvement in pain at Week 24 in early, seropositive RA patients with the SE HLA Class II risk alleles (ie, SE+). 	
 Mean change from baseline in SE+ participant-reported pain (VAS) at Week 24
Other Secondary	

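### The primary test (SE+ ACR50) uses no covariate, and Table 10.3.1-1 names no CI for its percentage-point difference: a cheap improvement, not an error

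*Combined protocol and SAP*

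**What the plan says.** Section 10.1 tests five endpoints in a fixed order at two-sided 5% and stops at the first failure. Step 1 is the primary endpoint, "Proportion of SE+ participants meeting ACR50 response at Week 24" (Table 4-1).

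Table 10.3.1-1 sets the models. Binary endpoints "will be analyzed with a logistic regression including treatment in the model", and "The OR along with its 95% CI will be provided". Two rules add terms. For the whole population, "the stratification variable SE +/- will also be included as a factor in logistic regression model". For a response defined by a cutoff on a continuous variable that was also measured at baseline, "the analysis model will also include the continuous baseline covariate". Changes from baseline go into a repeated-measures model with "covariate of corresponding baseline and baseline-by-day interaction". For these the table promises "The difference in adjusted LSMEANS between abatacept and adalimumab at the primary time point", with its 95% CI.

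Applied to the hierarchy:

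| Step | Endpoint | Baseline or stratum term | Effect measure with CI |
|---|---|---|---|
| 1 | ACR50, SE+ | none | odds ratio |
| 2 | DAS28-CRP remission, SE+ | baseline DAS28-CRP | odds ratio |
| 3 | ACR50, whole population | SE status | odds ratio |
| 4 | CDAI remission, SE+ | baseline CDAI | odds ratio |
| 5 | Change in pain, SE+ | baseline pain, baseline-by-day | difference in adjusted means |

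The result to be confirmed is stated on another scale. For the SE+ subgroup of study IM101567, Section 3.2.2 reports "estimate of difference % for ACR50 was 32 [95% CI 7 to 55". Section 5.4.2 justifies the primary endpoint by that 32-point difference and by an interval that excludes zero.

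**The concern.** The test on which the other four depend uses no baseline information, although baseline DAS28-CRP is collected and already enters the step 2 model. If that score predicts ACR50, prespecified adjustment keeps the type I error and buys some power or precision.

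The second point is the scale. Arm proportions give a crude difference by subtraction, but the table names no interval for it. The reader would then compare an odds ratio with an earlier result given as 32 points (7 to 55), or use an interval that was not prespecified.

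At stake are a little power at step 1 if the true effect is well below 32 points, and a headline result on the scale that motivated the trial. The validity of the test is not at stake.

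**Working it through.** **Inputs from the documents.** 150 per arm and about 3/4 SE+ (Section 10.1): 150 × 0.75 = 112.5, which agrees with the stated 112. Alpha is two-sided 5%. The earlier SE+ difference is 32 points, from 30 and 31 participants. The visible text gives no response rates or power for the primary test, so no stated power can be reproduced.

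**Assumptions.** Response of 45% vs 63% (18 points), 40% vs 60% (20 points) and 40% vs 72% (32 points). Baseline score with an odds ratio for response of 1.0 to 2.7 per SD. At 45% response, 1.35 corresponds to an AUC of 0.58, 1.65 to 0.63 and 2.7 to 0.74.

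**Unadjusted test by formula.** Standard error = √[p1(1−p1)/112 + p0(1−p0)/112]; power ≈ Φ(difference / standard error − 1.96).

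- 45% vs 63%: √[(0.2331 + 0.2475)/112] = 0.0655; 0.18/0.0655 = 2.75; power about 78%.
- 40% vs 60%: √[(0.24 + 0.24)/112] = 0.0655; 0.20/0.0655 = 3.05; power about 86%.
- 40% vs 72%: √[(0.24 + 0.2016)/112] = 0.0628; 0.32/0.0628 = 5.10; power about 99.9%. The CI width is 2 × 1.96 × 6.28 = 24.6 points.

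**Adjusted test by simulation.** 20,000 trials per row, standard normal baseline score, Wald tests. Simulation error of a power difference is about 0.2 points. Changes come from unrounded values.

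| OR per SD | 45% vs 63%: unadjusted / adjusted (change) | 40% vs 60%: unadjusted / adjusted (change) |
|---|---|---|
| 1.0 | 78.4 / 78.1 (−0.3) | 86.0 / 85.6 (−0.4) |
| 1.35 | 78.3 / 78.6 (+0.3) | 85.5 / 85.9 (+0.4) |
| 1.65 | 77.6 / 79.5 (+1.8) | 86.0 / 87.5 (+1.5) |
| 2.2 | 77.9 / 82.3 (+4.5) | 86.3 / 89.7 (+3.3) |
| 2.7 | 77.7 / 84.2 (+6.5) | 85.9 / 90.9 (+5.0) |

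Type I error at 45% in both arms was 4.9 to 5.3% unadjusted and 4.9 to 5.2% adjusted.

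**At 32 points.** Power is at least 99.8% either way. The SD of the estimated risk difference falls from 6.35 to 6.21 points at 1.65, worth 112 × (6.35/6.21)² = 117 per arm. At 2.7 it falls from 6.26 to 5.75, worth 112 × (6.26/5.75)² = 133 per arm. The median CI width falls from 24.5 to 23.9 points at 1.65 and from 24.6 to 22.5 at 2.7. If the score is not prognostic, the SD is 6.31 unadjusted and 6.32 adjusted: no gain.

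**Which test decides.** In the treatment-only model, Wald, likelihood-ratio and score tests were compared over all tables with 1 to 111 responders per arm. The probability that their 5% decisions differ was 0.0000 at 45/45, 60/45, 65/45 and 77/45%. Once an adjusted model is run as well, at 45% vs 63% the two models disagree in 5.6% of trials at 1.65 and 10.4% at 2.7.

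**Whole population (step 3), same covariate beside SE status.** 112 SE+ and 38 SE− per arm, differences of 18 and 3 points, 10,000 trials per row. The power change is −1.1, −0.4, +1.1, +3.9 and +6.1 points at 1.0, 1.35, 1.65, 2.2 and 2.7. The 3 points for SE− are close to (25 − 0.76 × 32)/0.24 = 2.8, from the overall and SE+ results and the 76% SE+ share in Section 3.2.2.

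**The case against.** The strongest reply is that this is a preference. ACR50 is a percentage improvement across seven components (Appendix 14). It has no single corresponding baseline value, so the cutoff rule does not reach it, and SE status is constant within SE+. Adding DAS28-CRP is a new choice and not the repair of an omission. That stands. A reader might infer from the table that the primary analysis is inconsistent or faulty; the documents do not support this, because the treatment-only test is valid and follows from the plan's rules.

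The benefit also rests on an input that the documents do not give. They nowhere say how well DAS28-CRP predicts ACR50, and at the 32 points to be replicated there is no power to gain. That stands too.

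On the interval, anyone with arm counts can calculate a crude difference and CI, and the table does not exclude further summaries. Part of Section 10.3.3 is redacted and no separate SAP text is available, so the claim reaches only Table 10.3.1-1. Within that limit it holds: an adjusted interval cannot be rebuilt from arm counts, and the purpose is to prespecify it.

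A reader might also infer that the plan leaves the deciding p-value open. It does not. It gives one model for this endpoint, and the usual tests of that model agree. The disagreement rates above arise only once a second model exists, so they are a reason to write the fix carefully and not evidence of a present ambiguity.

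Finally, changing a primary model during a trial has a credibility cost, and unblinding is not a clean milestone here. Both drugs are supplied open-label (Table 7-1), and participants and some site staff may know the allocation (Section 7.3). This stands and sets the timing of the fix.

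**Conclusion.** The point holds as a modest, inexpensive improvement. SE+ ACR50 is the only one of the five hierarchical tests without a covariate, and the table names no interval on the scale of the earlier 32-point result. The interval is useful whatever the covariate does.

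The value of the covariate depends on assumed response rates and prognostic strength. At a true difference of 18 to 20 points the power change runs from a loss of about 0.4 points (not prognostic), through a negligible gain (1.35 per SD) and +1.5 to +1.8 (1.65), to +5 to +6.5 (2.7, a strong predictor). At 32 points only the CI narrows, by about 0.6 points of width at 1.65 (24.5 − 23.9).

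A reader might infer that the same covariate belongs in the whole-population ACR50 model. That is not supported: there it loses power when the covariate is null or weak.

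**What to change.** By dated amendment of Table 10.3.1-1 and the SAP, before database lock and before any by-arm review of outcome data:

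1. Add continuous baseline DAS28-CRP to the SE+ ACR50 logistic model.
2. State that the treatment test in this adjusted model alone carries the step 1 p-value, and keep the treatment-only model as a sensitivity analysis.
3. Report the standardized risk difference with 95% CI beside the odds ratio and the arm proportions, as an estimate and not a second test. In the simulations its CI and the adjusted test disagreed in 0.5 to 0.7% of trials.
4. Define baseline DAS28-CRP once, for steps 1 and 2: last value before the first dose, with the screening value as fallback so that nobody is dropped. Section 9.4 asks for Day 1 results to be reviewed before randomization, but the visit order in Section 9 is only recommended, so the fallback should be written down.
5. Leave the whole-population ACR50 model as it is.

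The cost is a text amendment and a few lines of code, with no new data or visits. The odds ratio becomes conditional: at 45% vs 63% its median moves from 2.08 to 2.19 at 1.65 per SD and to 2.43 at 2.7, and its log-scale standard error from 0.273 to 0.283 and 0.305. It will no longer match the odds ratio implied by the arm proportions, which is one more reason to show the standardized risk difference. If DAS28-CRP is not prognostic, up to about 0.4 points of power are lost.

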10.3.2 Safety Analyses

The proportion (%) of participants with AEs, deaths, SAEs, AEs of special interest, and AEs leading to discontinuation and of participants with laboratory marked abnormalities will be provided by treatment group. Summaries for the SBTP will include events from the start of study treatment up to start of the OLTP for participants continuing in the OLTP or up to last dosing date +56 days for participants discontinuing during the SBTP using the as-treated analysis population. AEs of special interest are infections, malignancies, autoimmune disorders, and injection-site reactions. Summaries for the cumulative abatacept period will include safety events with onset on or after the first day of abatacept treatment in the study up to 56 days after the last abatacept treatment in the study using the cumulative abatacept population.

10.3.3 Other Analyses

[REDACTED]

10.3.3.2 Patient-reported Outcomes Analyses

For the individual components of the SF-36, WPAI-RA, and FACIT-F and duration of MS, changes from baseline will be summarized by treatment, and 95% CI for the treatment differences in changes from baseline will be constructed.

